7.5 Post Study Adverse Events

7.5.1 Non-serious Adverse Events

Adverse events that are identified at the last assessment visit (or the early termination visit) must be recorded on the AE eCRF with the status of the AE noted. These adverse events must be followed by the investigator until the events are resolved, events determined to be chronic or the subject is lost to follow-up. Resolution means the subject has returned to the baseline state of health, or the investigator does not expect any further improvement or worsening of the adverse event.

7.5.2 Serious Adverse Events

Serious adverse events that are identified on the last assessment visit (or the early termination visit) must be recorded on the AE eCRF page and reported to Perrigo according to the procedures outlined above. Subjects with unresolved previously reported serious adverse events, or any new serious adverse events identified on the last assessment visit, should be followed by the investigator until the events are resolved, or the subject is lost to follow-up. Resolution means the subject has returned to the baseline state of health, or the investigator does not expect any further improvement or worsening of the adverse event. The investigator should continue to report any significant follow-up information to Perrigo up to the point that the event has resolved. Any

serious adverse event reported by the subject to the investigator that occurs after the last assessment, and are determined by the investigator to be reasonably associated with the use of the study drug, should be reported to Perrigo.

8. STATISTICAL ANALYSIS

The sections that follow highlight sample size determination and the planned analyses for this study. A statistical analysis plan (SAP) will be prepared separately from this protocol which gives descriptions of the statistical methods, models, hypotheses and subject populations to be analyzed. The SAP will be completed and approved before locking the database and unblinding the study and will serve as a companion to the protocol and the *de facto* documentation of the proposed statistical evaluation. The SAP will be completed and finalized prior to breaking the blind.

8.1 Statistical Analysis Plan

8.1.1 Analysis Populations

The following populations are defined for the purpose of analyses:

- Intent-to-Treat (ITT) (safety population): Any subject that was randomized, received and used study medication.

- Modified Intent-to-Treat (mITT): Any subject, who met the inclusion/exclusion criteria, was randomized, received and used the study medication, and returned for at least one post-baseline efficacy assessment.

- Per Protocol (PP): Any subject who:
 - met inclusion/exclusion criteria,
 - was randomized, received and used study medication,
 - met the protocol criteria for compliance [REDACTED]
[REDACTED] and
 - completed Visit 4/Week 12/Day 84 (End of Treatment/Early Termination Visit) efficacy evaluations within the designated window (± 4 days) OR was discontinued from the study due to treatment failure and
 - had no significant protocol violations that could have interfered with the administration of the treatment or the precise evaluation of treatment efficacy.

[REDACTED]

[REDACTED]

[REDACTED]

8.1.2 Planned Analysis

The safety analysis will be performed for the ITT subjects. The efficacy analysis will be conducted on both the PP and the mITT subject populations. Two-sided hypothesis testing will be conducted. Resulting p-values less than 0.05 will be considered statistically significant. No adjustments of p-values for multiple comparisons will be made. No interim analyses are planned. SAS software will be used for all data analyses and tabulations.

The treatment response will be summarized by treatment group for the end-of-treatment evaluation.

The two primary efficacy endpoints will be the mean percent change from baseline to Visit 4/day 84/Week 12 in the inflammatory (papules and pustules) lesion counts AND the mean percent change from baseline to Visit 4/Day 84/Week 12 in the non-inflammatory (open and closed) lesions.

[REDACTED]

8.1.3 Sample Size Considerations

[REDACTED]

[REDACTED]

[REDACTED]

8.1.4 Efficacy Measures and Analysis

Clinical endpoints

The primary efficacy measure will be the mean percent change from baseline to Visit 4/Day 84/Week 12 in the inflammatory (papules and pustules) lesion counts AND the mean percent change from baseline to Visit 4/Day 84/Week 12 in the non-inflammatory (open and closed) lesion counts. The secondary efficacy measure will be the proportion of subjects with clinical success on the Investigator's Global Assessment (IGA) at Visit 4/Day 84/Week 12. Success is defined as an IGA score that is at least 2 grades less than the baseline assessment.

Equivalent efficacy

For the mean percent reduction from baseline in the inflammatory and non-inflammatory lesion counts, the Test treatment will be considered to be therapeutically equivalent to the Reference treatment if the 90% confidence interval on the Test-to-Reference ratio of means, calculated by Fieller's Method, falls within the interval 0.80 to 1.25. The treatment means and estimate of residual variance for the confidence interval calculation will come from an Analysis of Variance of the Test and Reference results using a statistical model containing terms for Treatment and Site.

For the proportion of subjects with clinical success, the Test treatment will be considered to be therapeutically equivalent to the Reference treatment if the 90% confidence interval on the difference between Test and the Reference proportions is contained within the interval -20% to +20%. The confidence interval will be constructed using Wald's method with Yates' continuity correction.

Superiority

For the percent reductions from baseline in the inflammatory and non-inflammatory lesion counts, each active treatment will be evaluated to determine if it has superior efficacy to that of the Vehicle at Visit 4/Week 12/Day 84 via an Analysis of Variance using a statistical model containing terms for Treatment and Site.

The proportion of subjects with clinical success for each active treatment will be compared to that of the Vehicle using a Z-test with Yates' continuity correction.

All hypothesis tests will be two-sided at a significance level of $\alpha = 0.05$, except confidence intervals which will be based on $\alpha = 0.1$ (e.g., 90% coverage).

8.1.5 Safety and Adverse Events Analysis

The frequency and percent of subjects with adverse events will be summarized by MedDRA system organ class and preferred term and by severity and relationship to study drug for all three treatment groups. The adverse events reported by at least five percent of the subjects in any treatment group will also be tabulated. The comparable safety of the Test and Reference treatments will be evaluated by statistical comparison of the proportion of subjects who reported any adverse events. The frequency and distribution of application site reactions of erythema, dryness, scaling/peeling, burning/stinging, erosion, edema, pain and itching will be summarized and compared descriptively. Safety comparisons will be performed only for the safety intent-to-treat population.

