15.2 Appendix B: Instructions for the Subject48

15.3 Appendix C: Face Diagram52

16. REFERENCES..... 53

STUDY SYNOPSIS

Title:	A Multi-Center, Double-Blind, Randomized, Vehicle-Controlled, Parallel-Group Study to Compare Perrigo UK FINCO’s Limited Partnership Adapalene and Benzoyl Peroxide Topical Gel 0.3%/2.5% to Galderma Laboratories, L.P. Epiduo® Forte (Adapalene and Benzoyl Peroxide) Gel,0.3%/2.5%, and Both Active Treatments to a Vehicle Control in the Treatment of Acne Vulgaris.
Study Period:	12 weeks (84 Days)
Study Medication:	
 1. Adapalene and Benzoyl Peroxide Topical Gel, 0.3%/2.5%, Perrigo UK FINCO Limited Partnership, [REDACTED] 2. Epiduo® Forte (Adapalene and Benzoyl Peroxide) Gel,0.3%/2.5%, manufactured by Galderma Laboratories, L.P. 3. Vehicle of test product, Perrigo UK FINCO Limited Partnership, [REDACTED]
Study Objectives:	To compare the safety and efficacy profiles of Perrigo UK FINCO’s Limited Partnership Adapalene and Benzoyl Peroxide Topical Gel, 0.3%/2.5% to Galderma Laboratories Epiduo® Forte (Adapalene and Benzoyl Peroxide) Gel, 0.3%/2.5%, in order to prove bioequivalence between them and to demonstrate the superior efficacy of the two active formulations over that of the vehicle in the treatment of Acne Vulgaris.
Study Design:	Subjects in this multi-center, double-blind, randomized, vehicle-controlled, parallel-group study will be admitted into the study only after written informed consent/assent (as applicable) has been obtained and after all inclusion/exclusion criteria have been met. Male and female subjects 12 years to 40 years of age, inclusive, with acne vulgaris [REDACTED] will be eligible for enrollment.
Study Population:	[REDACTED] healthy males and females, 12 to 40 years of age, inclusive, who meet the inclusion/exclusion criteria, will be enrolled to obtain [REDACTED] modified-Intent-To-Treat (mITT) and [REDACTED] per-protocol (PP) subjects.
Dosing:	Subjects will be randomized [REDACTED] to either the test product, reference product or vehicle treatment group, respectively, and will apply [REDACTED] the study medication onto each area of the face (forehead, chin, right cheek, left cheek and nose) [REDACTED] avoiding contact with the eyes, lips, inside your nose/nostrils, angles of the nose, broken skin areas and mucous membranes at approximately the same time once daily for 12 weeks. [REDACTED]

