2.2 Safety

Safety of the test and reference products will be compared by evaluating the nature, severity and frequency of their adverse event profiles. All adverse events that occur during the study will be recorded whether or not they are considered to be related to the study medication. Descriptions of reactions or complaints will include the approximate date of onset, the date the adverse event ended, the severity of the adverse event, and the outcome. Comparisons between the treatment groups will be made by tabulating the frequency of subjects with one or more adverse events (classified into MedDRA terms) during the study. Pearson's Chi-Square test or Fisher's Exact test, whichever is most appropriate, will be used to compare the proportion of subjects in each treatment group with any adverse event. The adverse events reported by at least five percent of the subjects in any treatment group will be summarized descriptively.

[REDACTED]

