5.6 Safety Variables and Analyses

Duration of Treatment and Medication Compliance

Number of applications, days of exposure (i.e. duration of treatment), and compliance rate will be summarized by treatment group using descriptive statistics. For each subject, the duration of treatment (days) will be calculated using the following formula:

$(\text{Date of last application of study medication}) - (\text{Date of first application of study medication}) + 1.$

Medication compliance rate (%) will be calculated for each subject as follows:

$(\text{Total number of applications used}) / (\text{Expected number of applications}) * 100\%.$

[REDACTED] For prematurely discontinued subjects, expected number of applications will be determined based on the expected number of applications by the time of discontinuation, i.e. overall duration of treatment. Descriptive summaries of exposure and medication compliance rate will be provided by treatment group for the ITT subjects.

Adverse Events

Adverse events (AEs) will be coded in MedDRA, version 20.0. Treatment-Emergent Adverse Event (TEAE) is defined as any AE occurs on or after application of the first dose of study drug. Number and percent of subjects reporting TEAEs will be tabulated by treatment group. Summaries will be presented by body system and preferred term for the ITT population, and further by severity and relationship to study medication. TEAEs reported by 5% or more subjects for any treatment group will be summarized by preferred term. In the summaries of incidence rates (frequencies and percentages), severity and relationship to study drug, subjects who report more than one event that are mapped to the same preferred term will be counted only once under the strongest severity and relationship, accordingly. The difference between Test and Reference treatments with regard to severity and frequency of their dermatological adverse events will be statistically evaluated using Chi-Square or Fisher's exact test to compare the proportions of subjects of the two active treatment groups who report any TEAE.

Treatment-Emergent Serious Adverse Events (TESAEs) will be discussed within the clinical study report. TEAEs, TESAEs and TEAEs that led to treatment interruption or discontinuation will be presented in data listings.

Concomitant Medications and Vitals Signs

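### Test-versus-Reference safety comparability rests on a test of no difference, and the readable plan gives no difference estimate, confidence interval or rule for a non-significant result

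*Protocol*

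**What the plan says.** Protocol 8.1.5 sets the question and the tool together: "The comparable safety of the Test and Reference treatments will be evaluated by statistical comparison of the proportion of subjects" with any adverse event. Protocol 2.2 names the tool. Pearson's chi-square or Fisher's exact test, whichever suits, "will be used to compare the proportion of subjects in each treatment group with any adverse event". SAP 5.6 (Adverse Events) limits it to the two actives and uses a chi-square or Fisher's "exact test to compare the proportions of subjects of the two active treatment groups who report any TEAE". The decision level is in Protocol 8.1.2: "Two-sided hypothesis testing will be conducted. Resulting p-values less than 0.05 will be considered statistically significant". SAP 5.1 repeats it.

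The efficacy side is built differently. Protocol 8.1.4 and SAP 5.5 judge equivalence by placing a 90% confidence interval inside fixed limits: 0.80 to 1.25 for the lesion-count ratios, and -20% to +20% for the difference in IGA success. IGA success is a binary endpoint, like any adverse event.

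Protocol 8.1.3 and SAP 3.2 (sample size) are redacted, as is the allocation ratio. Text is also redacted at the end of Protocol 2.2 and in the Safety row of the synopsis. Protocol 8.1.5 and the Adverse Events part of SAP 5.6 show no redaction.

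**The concern.** The null hypothesis of the planned test is that the two proportions are equal, which is the very statement that a comparability claim would rest on. Failing to reject it does not support it. The logic also runs the wrong way with sample size: the fewer subjects or events there are, the easier it is to get p ≥ 0.05, and the more alike the products appear.

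The study objective (synopsis; SAP 2) is to compare both safety and efficacy profiles, so the report will have to say something about comparative safety. If the only inferential result is a p-value, a non-significant one may be taken as support for comparability when the data are also compatible with a materially higher event rate on Test. Nothing in the readable text guards against that.

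**Working it through.** **No figure to reproduce.** The documents give no readable sample size, power, expected adverse event rate or safety margin. Everything below is illustrative. It assumes equal Test and Reference arms of 200 to 400 subjects and any-AE proportions of 10% to 25%. Only the two-sided 0.05 level comes from the documents.

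**1. One non-significant result.** Assume 20/200 (10%) on Reference and 30/200 (15%) on Test.

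- Pooled proportion = 50/400 = 0.125. Null SE = √(2 × 0.125 × 0.875 / 200) = 0.0331. z = 0.05 / 0.0331 = 1.51, so chi-square p = 0.13. Fisher's exact p = 0.17.
- Unpooled SE = √(0.10 × 0.90/200 + 0.15 × 0.85/200) = 0.0330.
- 90% Wald interval: 0.05 ± 1.645 × 0.0330 = -0.4 to +10.4 points.
- 95% Wald interval: 0.05 ± 1.96 × 0.0330 = -1.5 to +11.5 points.

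The test is non-significant, yet the data allow an excess of about 10 points over an observed Reference rate of 10%. The p-value alone does not convey this.

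**2. How often a real difference gives p ≥ 0.05.** Power = Φ[(|p_T - p_R| - 1.96 × SE_null) / SE_alt], with the pooled SE under the null and the unpooled SE under the alternative. For 10% vs 15% at 200 per arm: (0.05 - 1.96 × 0.0331) / 0.0330 = -0.45, so power is 33%.

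| True rates (Reference vs Test) | 200 per arm | 300 per arm | 400 per arm |
|---|---|---|---|
| 10% vs 15% | 33% | 46% | 57% |
| 20% vs 25% | 22% | 31% | 40% |
| 10% vs 20% | 80% | 93% | 98% |

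A true excess of 10% to 15% would therefore be non-significant in about 67%, 54% and 43% of trials. A doubling from 10% to 20% would be missed in about 20%, 7% and 2%. For 80% power the test needs 686 per arm for 10% vs 15%, and 199 for 10% vs 20%.

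**3. What an interval would show.** With equal true rates of 10%, the 95% half-width is 1.96 × √(2 × 0.1 × 0.9 / n): 5.9 points at 200 per arm, 4.8 at 300 and 4.2 at 400. The report could then state the largest excess on Test that the data still allow.

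**4. The two parts of the plan side by side.** For IGA success the plan asks for an interval on the Test-minus-Reference difference and says what result counts as equivalence. For any adverse event, between the same two arms, the operative sections ask only for a p-value and say nothing about how to read it.

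**The case against.** The strongest reply is that the plan writes decision rules where it wants them. SAP 5.5 says what conclusion each rejected null supports, and the safety section has no such rule. SAP 5.6 speaks of evaluating a difference and does not use the word comparable, so a difference test fits its wording. This stands in part. A reader might infer that the plan treats p ≥ 0.05 as proof of comparability, but no section says so. Protocol 8.1.5 does attach comparability to this test, however, and no readable text closes off the misreading.

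A reader might also infer that the trial is too small for this comparison. The documents do not support that as a finding, because the sample sizes are redacted. The synopsis expresses the enrolment target as "modified-Intent-To-Treat (mITT) and [REDACTED] per-protocol (PP) subjects", which suggests sizing on efficacy but does not prove it. The power figures depend on the difference chosen: 5-point gaps look poor, while a doubling from 10% has about 80% power at 200 per arm.

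The p-value is also far from the whole safety evaluation. Adverse events are tabulated by MedDRA class and term, severity and relationship, with a separate table of events at 5% or more. Site reactions are summarised by visit, and serious events are discussed in the report. An imbalance would be visible in these tables, and an interval could be derived from the planned counts. That limits the consequence, but it leaves the planned inference unsuited to the stated question.

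Finally, an interval without a margin reports precision and does not establish comparability. That is correct, and the fix below takes it into account.

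**Conclusion.** The point holds as one of inference and reporting. The stated question is comparability, the only readable inferential tool tests for no difference, and a non-significant result from it does not answer the question at any sample size. The readable plan gives no difference estimate, interval, margin, interpretation rule or power for this comparison.

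Its numerical size cannot be fixed from the documents. Under the assumed arms of 200 to 400, a true 10% vs 15% would be non-significant in about 67% down to 43% of trials. A doubling from 10% to 20% would be missed in about 20% down to 2%. The diagnosis and the remedy do not depend on these figures.

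The comparison is supportive. The primary and secondary equivalence and superiority conclusions are unaffected. The correction is still worth making because it is nearly free and settles the interpretation before treatment assignments are known.

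**What to change.** In SAP 5.6, before unblinding:

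- Report the Test-minus-Reference difference in the proportion with any TEAE, with a two-sided 95% confidence interval (Newcombe or Miettinen-Nurminen), as the basis for the safety comparison. The 95% level pairs with the plan's two-sided 0.05 rule. The 90% level belongs to the efficacy equivalence tests, and no such test is made here.
- Keep the chi-square or Fisher p-value as descriptive.
- State that p ≥ 0.05 is not evidence of comparability, and that the report will quote the upper confidence limit.
- Because no margin is pre-specified, label the comparison descriptive and do not claim that comparability has been demonstrated.

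Align the wording of Protocol 8.1.5 at the next amendment. Protocol 10.2 requires permanent protocol changes to go through an amendment, so the SAP change should not wait for it.

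The cost is a few sentences in the SAP and one extra line of output. The downside for the sponsor is a slightly less favourable safety statement. No new data, subjects or change in conduct are needed.

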8.2 Comparability of Subjects at Baseline

Descriptive statistics will be presented, by treatment group, for subject baseline characteristics. The significance of any obvious treatment group differences will be discussed in the CSR.

9. CONSENT/ASSENT CONSIDERATIONS AND PROCEDURES

It will be made clear to the subject that, for the purposes of the study, they are consenting only for topical application of medication or vehicle. Investigators may discuss the availability of the study and the possibility for entry with a potential subject without first obtaining consent/assent. However, informed consent/assent must be obtained and documented prior to initiation of any procedures that are performed solely for the purpose of determining eligibility for research, including withdrawal from current medication(s). When this is done in anticipation of, or in preparation for, the research, it is considered to be part of the research.

The study must be approved in writing by an appropriate IRB as defined by FDA regulations. A copy of the Letter of Approval from the IRB, which also contains specific identification of the documents approved, must be received by Perrigo, prior to study commencement.

Periodic status reports must be submitted to the IRB at least annually as required by the site's IRB, as well as notification of completion of the study and a final report within three months of study completion or termination. A copy of all reports submitted to the IRB must be sent to Perrigo.

The investigator(s) has both ethical and legal responsibility to ensure that each subject being considered for inclusion in this study is given a full explanation of the protocol. This shall be documented on a written informed consent/assent form, which shall be approved by the same Institutional Review Board (IRB) responsible for approval of this protocol. Each informed consent/assent form shall include the elements required by FDA regulations in 21 CFR Part 50. The investigator agrees to obtain approval from Perrigo of any written informed consent/assent form used in the study, preferably prior to submission to the IRB.

Once the appropriate essential information has been provided to the subject and fully explained by the investigators (or a qualified designee) and it is felt that the subject understands the implications of participating, the IRB-approved written informed consent/assent form shall be signed by the subject (or their parent/legally authorized representative) and the person obtaining

consent/assent (investigator or designee). The subject shall be given a copy of the signed informed consent/assent form and the investigator shall keep the original on file.

If the subject fails to meet the inclusion/exclusion criteria at the conclusion of the screening phase, the subject will be withdrawn from screening. In the event that the subject is re-screened for study participation, a new informed consent/assent form must be signed.

